MATEC affiliated clinics in the Midwest region are eligible to participate in Aim 1 if meeting these criteria: (1) Clinic must have at minimum 40 current patients who are: racial/ethnic minority AND have a 'detectable' viral load AND are aged 16-35 years; (2) clinic must be willing to commit at least one staff person as lead for registering clients to receive the intervention, completing consent, and administering research surveys; (3) clinic must be willing to provide deidentified individual-level data for registered TXTXT participants, including viral load, retention in care (dates of clinic visits) at least twice per year; (4) clinic must not be using a competing medication reminder text messaging system; (5) clinic must be willing and able to rely on Lurie IRB. Once sites sign a memorandum of commitment, the study coordinator will schedule a conference call to conduct a standard of care questionnaire (Appendix K). The standard of care questionnaire will document existing clinic approaches to support adherence as well as any ancillary services (e.g., transportation assistance). This information will form a descriptive profile for each clinic.

Study Inclusion

For inclusion in the TXTXT intervention individuals must meet the following criteria: 1) diagnosed with HIV-infection and on ART regimen for at least one month (not new to ART); 2) aged 16-35 years; 3) have a viral load ≥ 200 c/mL and/or report poor adherence (<90% of pills taken in the last 30 days); 4) able to receive text messages; 5) provide informed consent for research component; and 6) are a patient of a participating clinic

Study Exclusion

Exclusion criteria includes: 1) those who are unable to give informed consent 2) those who are participating in other studies that impact primary and secondary outcomes.

Procedures for Recruitment and Informed Consent

Aim 1: Youth living with HIV (aged 16-35 years) who meet study inclusion criteria will be recruited by study staff from participating clinics. The EMR will identify potentially eligible patients who will be invited to complete further study screening and enrollment.

We will ask each clinic to construct a list of eligible patients and carefully track outreach, screening, and enrollment on an enrollment log provided. Clinics may enroll up to 50 participants (to account for 20% attrition, final sample of 40 participants per clinic).

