yet?" and "Don't forget!" The SMS platform is bi-directional and has an automated response system, so the participant is able to answer "1=yes" or "2=no" in response (press 1 or 2). When participants respond affirmatively, they will receive an encouraging message such as, "Great job!" However, when they respond with a "no" they will receive an acknowledging and encouraging message such as "You can do it!" (Appendix E).

Participants will be asked to complete a self-administered online survey at baseline, 3 months and 6 months post baseline. The survey will be hosted on REDCap and can be taken on a computer, tablet, or mobile phone. Participants will have the option of completing the survey remotely or coming to the clinic and taking the survey on-site (at a computer or tablet provided by the clinic). The online survey will be taken by both the intervention and comparison arm. The survey will measure demographics, self-reported ART adherence, HIV medication self-efficacy, barriers and facilitators of adherence, acceptability of TXTXT, and satisfaction (Appendix F). The survey CASI will be pilot tested with a small number of participants and adjusted as needed. Participants will also be asked to consent to release of specific EMR data to include viral load and attendance at HIV care visits.

At all study visits, staff will use the Fidelity Checklist to structure the visit and make sure that all procedures are followed (Appendix G). All study visits reflect the following general structure:

1. Complete intervention assessment
2. Complete standard-of care adherence counseling
3. Complete TXTXT Personalization form
4. Enter information into Dimagi platform (see Dimagi training, Appendix B)
5. Schedule date of next appointment
6. Build general rapport
7. Thank them for participation

As part of the initial visit, basic ART adherence education should be provided, based on the practices and/or protocols at each site. For example, if a site does not have a standard practice for adherence counseling, at a minimum staff should review:

1. The current list of medications prescribed to each participant and how each medication should be taken (make sure they know how to take their prescribed medication).
2. In addition, basic facts on the importance of adherence should be reviewed with each participant, such as those described here:
<https://aidsinfo.nih.gov/understanding-hiv-aids/fact-sheets/21/54/hiv-medication-adherence>

Retention

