Retention will be facilitated through obtaining contact information for the participant during the initial stages of the enrollment process. To minimize participant and staff burden, the follow-up visits can be conducted virtually. Participants will be sent a personalized link to complete the follow-up survey via REDCap. Of note, there will not be financial reimbursement for participation in the

intervention as the goal of the project is to understand how TXTXT will work in the “real world” and inform wide scale routine implementation. Prior studies by Drs. [name], [name], and [name] with vulnerable adolescent and other marginalized populations have maintained >80% retention. We will employ best practices in participant retention including: 1) collecting extensive locator information (multiple addresses/emails, phone numbers, social media profile names, etc.); 2) identification and discussion of difficult-to-reach participants and potential solutions during weekly team meetings; and 3) maintaining flexibility with mode of follow-up (e.g., in person options as well as internet based). The investigative team and participating clinic staff will review the study team’s retention plans and will be asked for guidance on how to best keep YYALH engaged in the study for at least 6 months. No financial incentives will be provided to youth participating in the TXTXT intervention trial (Aim 1). At 3 months, 6 months, and 12 months post baseline, electronic medical record (EMR) data from participating clinics will be used to determine viral load; retention in care will be assessed for up to 12 months post baseline.

STUDY DESIGN AND DATA ANALYSIS

Study participation summary

1. 12 participating clinics randomized 1:1 into intervention or comparison arm
2. 50 participants at each clinic enrolled and complete baseline survey; baseline EMR data pulled
3. Participants at intervention clinics begin TXTXT after baseline survey and continue for 6 months
4. All participants complete a 3-month survey
5. Participants at comparison clinics begin TXTXT after 3-month survey and continue for 3 months
6. All participants complete a 6-month survey; 6-month EMR data pulled
7. TXTXT intervention stops at 6 months post baseline for all participants
8. 12-month EMR data pulled

Timepoint	Who	What	Data collected
zero	12 participating clinics	Randomized 1:1 intervention: comparison arm	

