In order to assess feasibility, acceptability and satisfaction of the intervention we will use descriptive statistics using a combination of objective (e.g., rates of participation, intervention completion) and subjective measures (e.g., reported satisfaction, acceptability). In order to characterize adherence and retention in care throughout the course of the study, Kaplan-Meier survival curves will be used to measure time to adherence and retention, and Cox proportional hazard ratios will be used to assess whether individual-level factors are associated with shorter mean time to outcome. To measure reach of the intended participants, we will compare the study sample to those available in the sampling frame (proportion of those enrolled to those eligible). To measure adoption of clinic partners, we will evaluate the number of clinic partners who propose to continue with text messaging as adherence support post study (proportion of clinics who propose to continue TXTXT post study to total clinics). Satisfaction and acceptability will be measured by standard quantitative scales, summary total scores will be evaluated to determine whether or not ≥90% ratings were achieved.

Outcome definitions

Medication adherence: greater than or equal to 90% on self-reported visual analog scaler (non-adherence categorized at less than 90%)

Retention in care³³: two visits 90 days apart in the past year will be considered retained in HIV care

Viral suppression³⁴: VL < 200 copies/mL will be considered virally suppressed

Sample size, power calculation, and clinic scale up

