This questionnaire asks you how often you take your HIV medication. Some people get busy and forget to take their HIV medications or forget to carry their medications with them. Other times people find it hard to take their medications like their doctor told them to, such as “with food” or “on an empty stomach.” Other people decide to skip medications to avoid side effects (like feeling sick to your stomach) or to just not take their medications that day. It’s important for us to understand what people with HIV are really doing with their medications. For these questions, please report what you are actually doing. Don’t worry about it if you don’t take all of your medicine. We want to know what is really happening, not what you think we “want to hear.”

1. Do any of your HIV medications have special instructions, such as “take with food” or “on an empty stomach” or “with plenty of fluids?”

1 Yes 2 No (If NO, skip to question #2)

1. IF YES, how often did you follow those special instructions over the last four days?

Never	Some of the time	About half of the time	Most of the time	All of the time
 0	 1	 2	 3	 4

2. Some people find that they forget to take their pills on the weekend days. Did you miss any of your HIV medications last weekend—last Friday, Saturday or Sunday?

1 Yes 2 No

3. During the past 4 days, on how many days have you missed taking all doses of your HIV medications?

1. none
2. one day
3. two days
4. three days
5. four days

Now I'm going to ask you about the last 30 days. For all of your current HIV medications, what percent time (%) from 0 to 100 did you take your medication as prescribed in the last 30 days?

0% time would mean, "NONE of the time," 50% time would mean HALF of the time and 100% would mean ALL of the time. Numbers in-between would mean amounts between NONE and ALL of the time.

6. Please put an "X" on the line below at the point showing your best guess about how much you have taken these drugs in the **last 30 days**. [display VAS SCALE GRAPHIC].

NONE

ALL

The picture can't be displayed.

Treatment acceptability measure

Adapted from: <https://link.springer.com/content/pdf/10.1007/bf00960091.pdf>

How effective do you think this program (TXTXT) is might be?	1= very ineffective 2 3 4 5 6 7= very effective

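### Kaplan-Meier and Cox for time to adherence would describe first observed adherence at two surveys, not current adherence, and time to retention has no defined event or origin

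*Combined protocol and SAP*

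**What the plan says.** All references are to the combined protocol and SAP, Aim 1 unless stated.

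- **Method.** Data Analysis Plan and Variables: "Kaplan-Meier survival curves will be used to measure time to adherence and retention, and Cox proportional hazard ratios will be used", the purpose of the Cox models being "to assess whether individual-level factors are associated with shorter mean time to outcome". No event, time origin, censoring rule, relapse rule or tie method is given.
- **Adherence.** Outcome definitions: "Medication adherence: greater than or equal to 90% on self-reported visual analog scaler". The survey item in Appendix F asks "what percent time (%) from 0 to 100 did you take your medication as prescribed in the last 30 days".
- **When adherence is seen.** Procedures for Recruitment and Informed Consent: "Participants will be asked to complete a self-administered online survey at baseline, 3 months and 6 months post baseline".
- **Who enters.** Study Inclusion accepts a viral load of at least 200 c/mL, adherence below 90%, or both.
- **Retention.** Outcome definitions: "two visits 90 days apart in the past year will be considered retained in HIV care". Under Retention: "retention in care will be assessed for up to 12 months post baseline". The clinic site criteria require individual-level data, "including viral load, retention in care (dates of clinic visits) at least twice per year".
- **Effect of the intervention.** The same Data Analysis section assigns this to generalized linear models, with mixed-model and GEE versions for repeated measures, and says all models will allow for correlation within people and sites.

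**The concern.** Survival methods suit an event that happens at a known time and is then over. Adherence here is a current status, sampled at three fixed surveys, that can be gained and lost. Once a participant is counted as adherent at month 3, nothing at month 6 can bring the curve back down. A reader would naturally take a curve labelled as time to adherence for the level of adherence over the study, and would see too high a figure. The Cox results would depend on a software default for ties and be described as differences in mean time. For retention, a time-to-event analysis is promised for something defined only as a status over the past year. At stake is the description of adherence and retention over the study, and of the factors associated with them.

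**Working it through.** **1. The plan's own figure.** The plan gives no figure for the survival analysis. The related one is Table 2, which uses the correlation needed below (Sample size section: 6 sites per arm, 40 per site, two measures each, site correlation 0.05, within-participant correlation 0.2).

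- Design effect = 1 + (2 − 1) × 0.2 + 2 × (40 − 1) × 0.05 = 5.1.
- Observations per arm = 6 × 40 × 2 = 480; effective number = 480 / 5.1 = 94.1.
- Power for 45% against 65%, two-sided 0.05 (sidedness is not stated): 0.20 / √[(0.45 × 0.55 + 0.65 × 0.35) / 94.1] − 1.96 = 2.815 − 1.96 = 0.855, giving 0.80. Table 2 says 0.80.

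So 0.2 acts in the plan as the correlation between two binary measures on one person. Applying it to the month 3 and month 6 surveys is my assumption.

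**2. Curve against prevalence.** Let *p* be the prevalence of adherence, assumed equal at 3 and 6 months, and *r* the correlation. Assume no dropout between the surveys and everyone in the risk set.

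- Adherent at both: *p*² + *r p*(1 − *p*).
- Ever observed adherent by 6 months, which the curve estimates: 2*p* minus that.
- For *p* = 0.45, *r* = 0.2: both = 0.2025 + 0.2 × 0.2475 = 0.252; curve = 0.90 − 0.252 = 0.648.
- Month-3 successes no longer adherent at month 6: 1 − 0.252 / 0.45 = 44%.

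| Prevalence | Curve at 6 months, *r* = 0.2 | Reverted by month 6, *r* = 0.2 | Curve, *r* = 0.5 | Curve, *r* = 0.8 |
|---|---|---|---|---|
| 25% | 40% | 60% | 34% | 29% |
| 35% | 53% | 52% | 46% | 40% |
| 45% | 65% | 44% | 57% | 50% |
| 55% | 75% | 36% | 67% | 60% |

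The prevalences are the plan's control values. Correlations of 0.5 and 0.8 are assumptions to show the range. The excess equals the proportion adherent at month 3 but not at month 6, so it is never negative.

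**3. Ties.** With 480 analysable participants, *p* = 0.45 and *r* = 0.2, there are 480 × 0.45 = 216 events tied at month 3, 480 × (0.648 − 0.45) = 95 at month 6, and 169 censored. To see what this does to a hazard ratio, first-adherence times were simulated for 480 people with a two-level covariate (200 runs, exponential times, 35% adherent by 3 months in the reference group, seen only at 3 and 6 months, no reversal; the rate is assumed).

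| True hazard ratio | Cox, Breslow | Cox, Efron | Discrete-time complementary log-log |
|---|---|---|---|
| 1.5 | 1.36 | 1.48 | 1.50 |
| 2.0 | 1.66 | 1.97 | 2.02 |

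The Breslow values can be checked by hand. With all events tied at the visits, it estimates the ratio of per-interval risks: (1 − 0.65²) / 0.35 = 0.5775 / 0.35 = 1.65, and (1 − 0.65^1.5) / 0.35 = 0.476 / 0.35 = 1.36.

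**4. Mean time.** A hazard ratio compares rates. In step 3, 169 of 480 (35%) have no event when surveys end at 6 months, so an unrestricted mean time cannot be estimated from these data without assuming what happens later.

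**5. Time zero.** A viremic person reporting 90% or more meets Study Inclusion and has the event at baseline. The Appendix C screener (item 13) instead excludes anyone missing one dose or fewer in 7 days and fewer than three in the last month, with no viral-load exception. The two rules must be reconciled. The screener does not remove the problem: on once-daily dosing (assumed), three missed doses in 30 gives 27 / 30 = 90%, which passes the screener and counts as adherent.

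**6. Retention.** The definition looks back one year. Counting only visits after baseline, the status cannot be met before day 90. Counting earlier visits, it may be met on day 0. The plan does not say which applies.

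**The case against.** The strongest reply is that this is missing detail rather than a wrong method. Time to *first observed* adherence is a legitimate discrete-time quantity, and step 3 shows that Efron ties or a complementary log-log model recover the hazard ratio when there is no reversal. Retention rests on dated visits, from which a proper event could be built. The survival analysis is there to characterise outcomes; the effectiveness comparison and the power calculation rest on other models.

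Much of this stands. A reader might infer that the estimates are uninterpretable, but the documents do not support that: they can be interpreted as first observed adherence if defined and labelled so. A reader might also infer that retention cannot occur before day 90; that depends on a time origin the plan leaves open. The comparison clinics' start of TXTXT at month 3 does not invalidate the Cox models either, since these concern individual-level factors and exposure can enter as a time-varying term.

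What does not stand is that definitions alone suffice for adherence. Even well specified, the curve cannot fall, so it cannot describe adherence over the study. The text-reply logs do not fill the gap: comparison clinics have none before month 3, and replies are not the defined outcome.

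**Conclusion.** The concern holds for adherence as a mismatch between method and quantity, and for retention as a missing definition. At the plan's correlation of 0.2 and constant prevalence, the adherence curve overstates 6-month adherence by 15 to 20 percentage points across the plan's control values; at an assumed correlation of 0.8 the excess is about 4 to 5 points. The direction is certain and the size depends on how often people revert. The hazard-ratio attenuation (2.0 to 1.66) rests on an assumed event rate and on Breslow ties, which the plan neither chooses nor rules out. It would be wrong to infer that the trial's main result is compromised: the randomized comparison does not use these methods. The change should be made because a stated method would misdescribe the outcome and a suitable one is already in the plan.

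**What to change.** - **Adherence.** Replace Kaplan-Meier and Cox with the repeated-measures logistic model (GLMM or GEE) the plan already allows. Report prevalence at 3 and 6 months, with baseline adherence, arm-by-time and clinic effects, and individual-level factors as covariates.
- **If time to first adherence is still wanted.** Use a discrete-time complementary log-log model among those non-adherent at baseline, and label it first observed adherence.
- **Retention.** Analyse the defined 12-month status (retained or not) by logistic regression with a clinic effect. If a survival analysis is kept, build it from the dated visits and state the origin, event and censoring, including whether visits before baseline count.
- **Wording.** Remove the reference to mean time.

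The cost is a change of SAP text; the data are the same. The downside is that the time-to-event display is lost or relabelled, and a 12-month status uses less of the visit-date information than a dated event would.

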In this study we propose to use implementation science (IS) to scale up and evaluate the TXTXT evidence-based intervention (EBI) as an effective strategy to increase ART adherence and retention in HIV care, ultimately leading to a suppression of viral load among Black/African American, Hispanic/Latino and other racial/ethnic minority youth and young adults living with HIV (YYALH) participating in the intervention. We hypothesize that those who complete the TXTXT intervention will demonstrate a clinically meaningful increase in ART adherence, viral suppression, and sustained retention in care. Additionally, we hypothesize that the implementation of TXTXT will reach $\geq 80\%$ of the intended participants, will be fully adopted by $\geq 80\%$ of clinic partners, and will achieve $\geq 90\%$ ratings of satisfaction and acceptability. We will use mixed methods to complete our study aims: 1) determine the real-world efficacy of a regional scale up of an EBI – TXTXT -among poorly adherent racial/ethnicity minority YYALH, aged 16-35 years, on our primary outcomes: adherence and viral load suppression at 3-month post initiation of the intervention; and secondary outcome: retention in HIV care at 12-months post baseline, and 2) apply the Consolidated Framework for Implementation Research (CFIR) to describe the implementation process and identify barriers and facilitators needed to be addressed; and measure implementation outcomes of the TXTXT intervention using the RE-AIM framework (Reach, Efficacy, Adoption, Implementation, Maintenance). We will conduct a cluster randomized controlled trial to evaluate the intervention effectiveness (i.e., ART adherence, viral load suppression) at 3-months post-initiation of the intervention. Twelve clinic sites with the ability to enroll up to 50 participants at each site (N=600 participants total) will be trained to administer the TXTXT intervention. Sites will be randomized to either start the intervention immediately (i.e., intervention arm) or waitlisted to start at 3 months post baseline (i.e., comparison arm). In the comparison arm, the study will compare pre-post differences in adherence and viral suppression at 6 months post baseline. Last, we will evaluate retention in HIV care and sustained impact of the intervention at 12 months post baseline for all study participants.

RESEARCH TEAM

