Implementation Science is a critical new area of HIV prevention and intervention science which provides the frameworks and methods to effectively translate evidence to practice in the next era of HIV prevention intervention for public health impact.²³ As articulated by the CDC, a set of lessons learned from 20 years of diffusion of effective behavioral interventions (DEBI) and EBI projects will influence the next wave of dissemination and intervention initiatives. Implementation Science (IS) frameworks and methods provide the tools to incorporate these lessons into IS initiatives.²³ Furthermore, IS approaches allow us to measure systems-level HIV intervention implementation, a promising, but much rarer form of implementation.²⁴ By systematically studying the factors that influence implementation at higher levels of implementation, as well as evaluating specific implementation outcomes, we can shift our focus from intervention efficacy to public health impact among those populations most affected by the epidemic, including racial/ethnic minority youth.

IS approaches are necessary to understand and inform the roll out and scale up of effective strategies to increase ART adherence. IS studies have highlighted the need for multilevel interventions and diverse models of dissemination. Implementation science also provides relevant conceptual and measurement frameworks to guide a hybrid trial of clinical outcomes and implementation factors.²⁵⁻²⁸

The Reach, Effectiveness, Adoption, Implementation, and Maintenance (RE-AIM) framework is an evaluation and reporting scheme commonly used to examine the potential public health impact of an intervention.²⁹ Reach represents the number and representativeness of patients who participate out of the eligible patient population. Effectiveness is the impact of the intervention on participant outcomes.

Adoption is the number and representativeness of eligible staff/settings that agree to deliver the intervention out of all eligible staff/settings. Implementation is the fidelity to the intervention. Maintenance is the degree to which the intervention is sustained over time. RE-AIM provides a useful measurement framework for capturing both clinical and implementation outcomes within the same study.

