A total of 12 clinics and up to N=600 YYALH will be enrolled in this study for evaluation purposes. Each clinic will be able to enroll up to 50 participants for a maximum total of 600 participants. We assume a 20% attrition rate, and therefore the sample size available for analysis will be N=480. Sites will be randomized to either a 3-month observation (i.e., comparison arm) or an immediate start intervention arm; at the end of the first 3-month period comparison arm sites will start the intervention for the 3 months and intervention sites will continue the intervention for an additional 3 months (6 months total). Pre-post EMR data, SMS data, and participant satisfaction data will be collected to determine efficacy, durability, maintenance and satisfaction (see expected outcomes). Rapid interim data analysis and interpretation will occur at 3 months. In Year 3, all clinics and participants (in both the initial control arm or intervention arm) will have their medical records abstracted. In addition, de-briefing interviews will be conducted with clinic staff to assess implementation outcomes. Final analysis and sustainability plan will be conducted and elaborated.

This cluster randomized control study is powered to detect 20% difference in ART adherence (>90%) among participants receiving the TXTXT intervention and the control groups. The power is calculated based on 3 levels hierarchical model design (i.e., randomization at the site level, two measures for each participant). The correlations between the participants within the site is assumed to be 0.05 and correlation within a participant is assumed to be 0.2. The proportion of participants with $\geq 90\%$ ART adherence for the control group is assumed to be 25%, 35%, 45% and 55%. The effect size is assumed to be 10%, 20% and 25%. Given Type I error rate is 0.05, using the mixed model approach, the corresponding power is listed below.³⁵ The sample size with 6 sites in each arm and 50 participants from each site would have 80% power to detect 20% difference at 3 month post baseline.

Table 2: Power (6 sites in each arm, 40 participants from each site)

		proportion of participants with $\geq 90\%$ ART adherence (Control)			
Effect Size	25%	35%	45%	55%	
10%	0.30	0.29	0.28	0.29	
20%	0.82	0.80	0.80	0.83	
25%	0.95	0.94	0.94	0.96	

Track Lessons Learned

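### Adoption is measured as trial clinics' intention to continue TXTXT after the study, which conflicts with the protocol's own RE-AIM definition and leaves out eligible clinics that declined

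*Combined protocol and SAP*

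**What the plan says.** The Protocol Summary hypothesises that TXTXT will reach at least 80% "of the intended participants, will be fully adopted by" at least 80% of clinic partners. The term clinic partners is not defined.

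Aim 2 commits the study to measuring implementation outcomes with RE-AIM. The Implementation Science part of the Conceptual Framework states what the terms mean: "Adoption is the number and representativeness of eligible staff/settings that agree to deliver the intervention out of all eligible staff/settings", and "Maintenance is the degree to which the intervention is sustained over time".

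The Aim 1 section Data Analysis Plan and Variables then gives the working measure of adoption: "we will evaluate the number of clinic partners who propose to continue with text messaging as adherence support post study", expressed as the "proportion of clinics who propose to continue TXTXT post study to total clinics".

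Four other statements bear on this:

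- Sample size section: "A total of 12 clinics and up to N=600 YYALH will be enrolled in this study for evaluation purposes".
- Clinic site inclusion criteria: "MATEC affiliated clinics in the Midwest region are eligible to participate in Aim 1 if meeting these criteria". Five criteria follow, and sites sign a memorandum of commitment. The number of clinics meeting the criteria is not given.
- Study participation summary: "TXTXT intervention stops at 6 months post baseline for all participants".
- Sample size section again: EMR, SMS and satisfaction data are named as sources for several outcomes, maintenance among them, with a pointer to an expected-outcomes section that is not in the text supplied.

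**The concern.** The framework section and the analysis plan give adoption two different meanings. In the first it is the uptake of TXTXT among clinics that could have taken it up. In the second it is the wish of clinics already in the trial to carry on afterwards. Every clinic in the second measure has already met a willingness criterion and signed a commitment, so a clinic that was eligible and said no cannot affect the result.

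The project is presented as a regional scale-up and a step towards wider dissemination. Which clinics take TXTXT up, and how they differ from those that do not, is therefore one of its main implementation questions. A report that at least 80% of clinics adopted TXTXT would be read as answering that question, when the figure behind it would be a statement of intent by participating clinics.

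The same paragraph of the analysis plan measures reach as those enrolled out of those eligible, in line with the framework. Only adoption loses its eligible denominator.

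**Working it through.** The documents give no sample size, power or expected count for the adoption hypothesis, so there is no stated figure to reproduce. The check compares the definitions and then does simple arithmetic.

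**Definitions side by side**

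| Element | Implementation Science section | Aim 1 analysis plan | Protocol Summary hypothesis |
|---|---|---|---|
| Numerator | Settings and staff agreeing to deliver | Clinics proposing to continue after the study | Clinics that fully adopt (not defined) |
| Denominator | All eligible settings and staff | Total clinics | Clinic partners (not defined) |
| Representativeness | Included | Not mentioned | Not mentioned |

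If total clinics and clinic partners both mean the 12 trial clinics, the second and third columns share a denominator, and the first column differs from both. The numerator of the second column differs from the first. It is closest to sustainment, but it is only an intention, because TXTXT stops for everyone at 6 months.

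**Inputs**

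- Trial clinics: 12 (sample size section).
- Threshold: 80% (Protocol Summary).
- Eligible clinics, E: not in the documents; every value below is an assumption.

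**Step 1. The threshold on the plan's measure.** 0.80 × 12 = 9.6, so at least 10 clinics are needed. 10/12 = 83.3% meets it; 9/12 = 75.0% does not.

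**Step 2. The framework measure.** Assume that the 12 trial clinics are exactly those that agreed. Adoption is then 12/E, and 12/E ≥ 0.80 requires E ≤ 12/0.80 = 15.

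| Assumed E | 12/E | 80% or more? |
|---|---|---|
| 12 | 100% | yes |
| 13 | 92% | yes |
| 15 | 80% | yes |
| 16 | 75% | no |
| 20 | 60% | no |
| 24 | 50% | no |

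**Step 3. Changing the numerator alone.** If agreement to deliver replaces intention to continue but the 12 trial clinics stay as the denominator, the result is 12/12 = 100% by construction. Numerator and denominator have to change together.

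**Step 4. How coarse the threshold is.** For 10 of 12 the exact (Clopper-Pearson) 95% interval is 51.6% to 97.9%, and even 12 of 12 has a lower limit of 73.5%. With X binomial (12, p), P(X ≥ 10) is 25% for p = 0.70, 56% for p = 0.80 and 89% for p = 0.90. These figures do not decide the question of definition. They show that the 80% can serve only as a descriptive marker.

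**The case against.** The best defence is that the study may define adoption for its own purposes and has done so openly. Texting ends for everyone at 6 months, so a clinic's proposal to carry on is a decision to take TXTXT up outside the trial, which is a fair reading of full adoption. The measure can also fail, whereas sign-up among trial clinics cannot. In addition, joining meant accepting trial requirements: reliance on the lead IRB, data sharing, a staff lead for consent and surveys, and at least 40 qualifying patients. A clinic might want TXTXT and be unable to meet those terms, so sign-up is an imperfect measure of uptake too.

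Much of this stands. It shows that intention to continue is worth reporting and that a sign-up measure needs caveats. It does not remove the conflict, because the protocol adopts RE-AIM, states its definition of adoption and then measures something else without saying so.

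Four stronger readings might be inferred, and the documents do not support them:

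- That the 80% hypothesis has the wrong denominator. As worded it refers to clinic partners, which the analysis plan's denominator fits.
- That the framework itself calls this quantity maintenance. It defines maintenance as being sustained over time; a proposal to continue is at most a proxy for that.
- That maintenance has no measure at all. Data sources are named for it, sustained impact is evaluated at 12 months, and a sustainability plan is promised. What is missing, in the text supplied, is a defined clinic-level measure.
- That the hypothesis is formally tested. No test is planned.

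**Conclusion.** The conflict between the framework definition and the analysis plan is real and should be resolved. It limits what the trial can say about regional uptake, and a reader of the adoption result would probably misunderstand it. It concerns a descriptive implementation outcome and leaves the comparison of adherence and viral suppression untouched, so it is a correction worth making rather than a threat to the trial.

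The size of the difference is unknown. Whether the two measures would fall on opposite sides of 80% depends on E. A reader might infer that true adoption must be low, around 40% to 60%, but that would need 20 to 30 eligible clinics (12/30 = 40%, 12/20 = 60%), a count found nowhere in the documents. Nor can the 13 Ryan White clinics in MATEC's practice transformation cohort be taken as E: eligibility is set by MATEC affiliation and the five criteria, and the Innovation section expects clinics outside that programme as well. Enrolment is also fixed at 12 by design, so a low 12/E could reflect a full trial rather than refusals.

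**What to change.** 1. Keep a site-recruitment log of MATEC-affiliated clinics that were eligible, approached, agreed, declined (with reasons and basic characteristics) and delivered TXTXT.
2. Report adoption as clinics that agreed and delivered, out of eligible clinics approached. Give the total number eligible beside it, compare adopters with decliners, and note that enrolment was capped at 12 and that joining also meant accepting trial requirements.
3. Report the share of the 12 clinics proposing to continue separately, labelled as intention to sustain. State who is asked, when, and with what question; the staff interview guide as supplied in Appendix J has no such item.
4. State in advance that the descriptive 80% threshold for clinic partners, at least 10 of 12, applies to intention to continue, or else set a threshold for the framework measure. Define clinic partners and total clinics.
5. If the sponsor prefers to keep the present measure under the name of adoption, say plainly that it departs from the RE-AIM definition given in the protocol.

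The cost is a few sentences of protocol text, one question to each clinic and a small log, some of which may have to be rebuilt from recruitment records. The adoption figure may turn out less favourable. Sample size, randomisation and the primary analysis do not change.
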